12.9 End of Study

The study will end after the last subject yet to complete the last Long-Term Follow-Up visit (Week 260) does so, has transferred to another BMN 270 study, is withdrawn from the study, or discontinues from the study. BioMarin reserves the right to discontinue the study any time for clinical or administrative reasons and to discontinue participation of an individual Investigator or site for clinical or administrative reasons, including, but not limited to, poor enrollment or noncompliance with procedures of the protocol or GCP. In addition, the study

Page 97

may be terminated if, in the opinion of BioMarin, the safety of the study subjects may be compromised.

Page 98

13 DATA QUALITY ASSURANCE

BioMarin personnel or designees will visit the study site prior to initiation of the study to review with the site personnel information about the IP, protocol and other regulatory document requirements, source document requirements, eCRFs, monitoring requirements, and procedures for reporting AEs, including SAEs.

At visits during and after the study, a CRA will monitor the site for compliance with regulatory documentation, with a focus on accurate and complete recording of data on eCRFs from source documents, adherence to protocol, randomization (if applicable), SAE reporting and drug accountability records.

Data quality control and analysis will be performed by BioMarin or a designee, based on a predefined analysis plan.

Page 99

14 STATISTICAL METHODS AND DETERMINATION OF SAMPLE SIZE

14.1 Statistical and Analytical Plans

The statistical analysis plan (SAP) will provide additional details on the planned statistical analysis. Unless otherwise stated, all analyses will be performed using SAS.

14.1.1 Interim Analyses

An interim analysis is planned after 20 treated subjects have completed the Week 26 visit (or have discontinued study participation prior to Week 26).

The primary efficacy endpoint for the interim analysis is change in the hFVIII activity, as measured by one-stage clotting assay, during Weeks 23-26 post-BMN 270 infusion from baseline. Each subject's hFVIII activity during Weeks 23-26 is defined as the median of the values obtained during this 4-week window. Values for hFVIII activity will be excluded if obtained within 72 hours since the last infusion of exogenous FVIII protein concentrates. A 2-sided one-sample t-test will be used to test the null hypothesis that the change is 0 or less against the alternative hypothesis that the change is greater than 0. In addition, subjects' hFVIII activity post-Week 23, defined as the median of the values obtained from Week 23 to the time of last follow-up, will be analyzed similarly as an important sensitivity analysis, utilizing additional data beyond Week 26. Descriptive summaries of the proportions of subjects whose FVIII activity during Weeks 23-26 and from Week 23 to the time of last follow-up is greater than or equal to select thresholds, such as 15, 25 and 30 IU/dL, and the confidence intervals of the proportions will be provided, respectively. The FVIII activity as measured by chromogenic assay will be analyzed similarly, as a supportive analysis.

The Hochberg procedure will be used to adjust for multiplicity of the interim analysis at Week 26 and the final analysis at Week 52 of the primary efficacy endpoint. (Regardless of the interim analysis results, the study will continue and the final analysis will be performed at Week 52.) At the final analysis at Week 52, the secondary efficacy endpoints will be tested hierarchically; the level of significance will be determined by the truncated Hochberg procedure for parallel gatekeeping. These multiple comparison procedures are described in greater detail in Section 14.2.

The secondary and tertiary endpoints will be summarized descriptively at the interim (Week 26) analysis.

Page 100

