			change from baseline) in this subgroup Repeat the primary analysis of FVIII activity (FVIII activity change from baseline at Week 104) in this subgroup
Washout period between the last dose of FVIII prophylaxis following gene therapy and the start of EEP	No washout period	3 days	Based on the half-life of the original FVIII prophylaxis product: • 3 days for standard half-life or plasmaderived products • 5 days for extended half-life
Definition of AEs/SAEs related to IS		All AEs/SAEs during or within 2 weeks' post-IS use	All AEs/SAEs following IS use up to each subject's last visit for the analysis
IS (CS or AIS) therapy to be included in the analysis		Systemic IS (CS or AIS) indicated for ALT elevation of any duration, or indicated for other purposes with a duration of at least 4 weeks	Systemic IS (CS or AIS) indicated for any purpose of any duration
Definition of an IS course (cycle)		The start of an IS use through the end of taper or increase in IS dose for ≥ 2 consecutive weeks preceded by at least 2 decreases in IS dose, whichever occurs earlier	The time period between the first day of starting an IS therapy to the last day of IS use. Any increase in the dose of IS will be considered as a new cycle of IS therapy with the first day of increase of IS dose constituting as the start day of a new cycle.

Comment(s)/ Recommendation(s):

This NTF serves as a bridging document between the analysis methods in the 270-301 protocol (version 7.0, 15 July 2021; US-specific), the 2-year analysis SAP (version 2.0, 13 December 2021) and the 2-year 270-301 CSR.

16-Mar-2023 | 5:35 PM PDT

PI , MD, PhD
PI , Clinical Sciences
BioMarin Pharmaceutical Inc.

PI , Regulatory Affairs BioMarin Pharmaceutical Inc.

CLINICAL STUDY PROTOCOL

Study Title: A Phase 3 Open-Label, Single-Arm Study To Evaluate The Efficacy

and Safety of BMN 270, an Adeno-Associated Virus Vector— Mediated Gene Transfer of Human Factor VIII in Hemophilia A Patients with Residual FVIII Levels ≤ 1 IU/dL Receiving

Prophylactic FVIII Infusions

Protocol Number: 270-301

Active Investigational Product: AAV5-hFVIII-SQ

IND/European Union Drug Regulating Authorities Clinical Trials (EudraCT) Number: 2017-003215-19 IND #: 017659

Indication: Hemophilia A

Sponsor: BioMarin Pharmaceutical Inc.

[name]

Development Phase: Phase 3

Sponsor's Responsible Medical

Monitor:

MD, MPhil

BioMarin Pharmaceutical Inc.

[name]

Duration of Subject

Participation:

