7 INTRODUCTION

Hemophilia A (HA) is an X-linked recessive bleeding disorder that affects approximately 1 in 5,000 males (Nathwani, 1992, Baillieres Clin.Haematol.). It is caused by mutations in the factor VIII (FVIII) gene that codes for FVIII protein, an essential cofactor in the coagulation pathway. Clinical manifestations of severe FVIII deficiency are frequent unprovoked bleeding episodes in joints and soft tissues causing permanent disability and occasionally death mostly after brain hemorrhage. Treatment in Western countries (Berntorp, 2012, Haemophilia.) consists of intravenous injection of plasma-derived or recombinant FVIII protein concentrates at the time of a bleed to control it or prophylactically to prevent bleeding episodes. The short half-life for FVIII (~8-12 hours) necessitates frequent infusions and makes this treatment prohibitively expensive for the majority of the world's hemophilia A patients. These individuals develop debilitating arthropathy and have a substantially increased risk of death from hemorrhage in life (Stonebraker, 2010, Haemophilia.). Chemical modification or bioengineering of FVIII may improve half-life to 18-19 hours (Kaufman, 2013, Blood). However, these extended half-life FVIII variants do not eliminate the need for lifelong FVIII protein administration (Hay, 2012, Blood).

Gene therapy offers the potential of disease-modifying therapy by continuous endogenous production of human FVIII (hFVIII) following a single administration of vector. Hemophilia A is well-suited for this approach because its clinical manifestations are attributable to the lack of a single gene product (FVIII) that circulates in low amounts (100-200 ng/ml) in the plasma. Tightly regulated control of gene expression is not essential, and a modest increase in the level of FVIII (a plasma level of 2 ng/ml protein leads to a 1% expression) can ameliorate the severe phenotype (Srivastava, 2013, Haemophilia.); thus, the therapeutic goal for gene therapy is a modest increase in hFVIII. Finally, the consequences of gene transfer can be assessed using simple quantitative rather than qualitative endpoints that can be easily assayed in most clinical laboratories.

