Treatment of severe HA presently consists of intravenous injection of plasma derived or recombinant human FVIII protein (rhFVIII) concentrates both as prophylaxis 2-3 times per week, and at the time of a bleed, to prevent or control bleeding episodes, respectively. The half-life for FVIII (12 to 18 hours for most approved products) necessitates frequent infusions, and although a major advance in the treatment of HA, it remains common for severe HA patients to continue to have multiple bleeding events on prophylactic therapy (median ABR of 1-4 with prophylaxis treatment in a recently published retrospective observational study (Berntorp, 2016, Haemophilia) and between 1-2 in 6 prospective FVIII interventional studies) and on-demand-only therapy (median ABR of 4.5-18 in a recently published retrospective study (Berntorp, 2016, Haemophilia) and between 20-60 in 6 prospective FVIII interventional studies). The consequence of multiple bleeding events is the development of debilitating multiple-joint arthropathy and substantially increased risk of death. Chemical modification (eg, direct conjugation of polyethylene glycol (PEG) polymers) and bioengineering of FVIII (eg, FVIII-Fc fusion proteins) improve half-life by approximately 50%, and thus, show promise in reduced dosing and maintaining activity levels above 1% trough for a greater proportion of the dosing interval. However, these extended half-life FVIII variants remain dependent on multiple infusions to maintain critical levels of FVIII activity in severe HA patients. There is therefore a strong unmet need for a fully preventive treatment of HA to give patients a FVIII level compatible with a normal and hemorrhage-free life.

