Documentation of bleeding episodes and FVIII usage for previous 12 months (by either subject or clinical information)	X	X	X	
Distribution of subject diaries and training in their use ^l	X			
Electrocardiogram	X			
Liver Ultrasound	X			
hFVIII Assays ^b	X	X ^j	X	
AAV5 TAb Assays ^c	X	X	X	X
AAV5 TI Assay			X	
Screen for Hepatitis B, Hepatitis C, HIV ^d	X			
Blood chemistry, hematology, and coagulation tests ^e	X	X	X	
Fasting lipid panel (blood triglycerides, total cholesterol, HDL cholesterol, and LDL cholesterol)				X
Urine Tests ^e	X	X	X	
Liver Function Tests ^e	X	X	X	

	Pric	or to BMN 270 Infusion		BMN 270
Assessment	Screening* (Day -28 to Day -1)	Smart Rescreening ⁱ (Day -28 to Day -1)	Baseline (Day -7 to Day -1)h	Infusion Visit (Day 1)k
PBMC collection (for baseline determination of AAV5 and FVIII specific cellular immunity)			X	
Von Willebrand Factor Antigen (VWF:Ag)			X	
Direct Thrombin Activity Test ^g			X	
TGA Assay ^g			X	
PCR of vector DNA in blood, saliva, urine, semen, and stools			X	X
Biomarker testing ^f	X			
Exploratory biomarker assessments ^g			X	
Haemo-QOL-A assessment			X	
EQ-5D-5L			X	
HAL			X	
WPAI+CIQ:HS			X	
PROBE			X	
BMN 270 Infusion				X

^{*} Screening assessments should be performed within 28 days of BMN 270 infusion (and must be performed within 42 days prior to BMN 270 infusion).

^a Complete physical examination should be done at Screening. Brief physical examination may be done at Baseline and at the BMN 270 Infusion Visit.

b Includes baseline FVIII activity (chromogenic FVIII assay and one-stage clot FVIII assay), coagulation exploratory assay, hFVIII inhibitor level (Bethesda assay with Nijmegen modification), hFVIII total antibody titer, and hFVIII protein assay. Baseline activity should be assessed at trough (at least >72 hours after last dose of replacement FVIII therapy, or 5x the known half-life of the FVIII concentrates administered).

^c Sample collection on the day of the infusion visit must be performed before the BMN 270 infusion is given. Screening, Smart Re-screening, and Infusion Day samples will be tested in an AAV5 Tab pre-screening assay specifically developed for enrolment purposes. Baseline and all post-dose samples will be tested in a different AAV5 Tab post-dose immunogenicity monitoring assay

^d Patients with documented negative results within the last 30 days do not need to be retested.

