9.7.2 Primary Efficacy Variables

9.7.2.1 FVIII Activity

The primary efficacy variable is change of the hFVIII activity, as measured by one-stage clotting assay, during Weeks 49-52 post-BMN 270 infusion from baseline. Each subject's hFVIII activity during Weeks 49-52 is defined as the median of the values obtained during this 4-week window. Values for FVIII activity will be excluded if obtained within 72 hours since the last infusion of exogenous FVIII protein concentrates.

Page 62

If a subject has used FVIII within 72 hours of a measurement day, all efforts should be made to obtain FVIII activity measurements when a 72-hour interval without FVIII use is achieved; The 72-hour wash-out period is only intended for subjects who have achieved $FVIII \ge 5 \text{ IU/dL}$ at 16 weeks after BMN 270 infusion and who have not resumed FVIII replacement therapy.

In the event of an FVIII activity level decline during the study:

- If FVIII activity has declined at least 20% from the peak but less than 35% and has declined for at least 2 consecutive assessments, FVIII activity and LFTs should be repeated every 7 days until FVIII activity is stable or increasing
- If FVIII activity has declined >35% from the peak and has declined for at least 2 consecutive assessments, FVIII activity and LFTs should be repeated every 72 hours until FVIII activity is stable or increasing

In subjects who show an initial response to BMN 270 but who later have FVIII activity decline to < 5 IU/dL, the investigator and medical monitor will review the subject's FVIII activity levels and discuss whether to resume prior FVIII prophylaxis. In addition, the investigator will notify the subject of his FVIII activity levels and will discuss with the subject the risk of bleeding and when (and if) prior FVIII prophylaxis will be resumed.

Note that fluctuations in FVIII activity are common, and if no clear trend indicating a decline in FVIII activity is observed, then this additional testing may be deferred (upon consultation between the Investigator and the Medical Monitor) until either a more clear trend of decline has been demonstrated or until the FVIII activity levels stabilize or increase.

Details on collecting FVIII activity samples are included in the Laboratory Manual.

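### Amendment 1's flat 72-hour exclusion can let residual extended half-life FVIII into post-infusion activity values, and the baseline rule does not say whether 72 h or 5 half-lives governs

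*Protocol*

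**What the plan says.** All references are to Amendment 1 (25 January 2018) unless stated otherwise.

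- **Post-infusion, interim endpoint (Weeks 23-26), Section 14.1.1 and Synopsis:** "Values for hFVIII activity will be excluded if obtained within 72 hours since the last infusion of exogenous FVIII protein concentrates".
- **Post-infusion, primary endpoint (Weeks 49-52), Section 9.7.2.1 and Synopsis:** "Values for FVIII activity will be excluded if obtained within 72 hours since the last infusion of exogenous FVIII protein concentrates". Section 9.7.2.1 then says that the 72-hour wash-out is meant only for subjects who reached at least 5 IU/dL at 16 weeks and have not gone back on FVIII replacement. It does not say what happens to values from other subjects, and Section 14.1.1 does not mention the limit.
- **Baseline, Table 9.1.1 footnote b (Section 9.1):** sampling at trough, "at least >72 hours after last dose of replacement FVIII therapy, or 5x the known half-life of the FVIII concentrates administered". The two conditions are joined by *or*, with no statement of which prevails.
- **Half-lives:** Section 7 gives "The short half-life for FVIII (~8-12 hours) necessitates frequent infusions" and, for modified products, "Chemical modification or bioengineering of FVIII may improve half-life to 18-19 hours". Section 7.3 gives a different range: "The half-life for FVIII (12 to 18 hours for most approved products) necessitates frequent infusions", and says that modification lengthens half-life by about 50%.

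The subject's value is the median within the 4-week window. The proportions of subjects reaching thresholds such as 15, 25 and 30 IU/dL are described as well (Sections 14.1.1 and 14.2).

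**The concern.** The endpoint is meant to measure FVIII made by the transgene. The exclusion rule is what keeps infused factor out of it, and a fixed 72 h does this equally well for all products only if their half-lives are similar. The protocol's own figures say they are not. No listed entry criterion excludes users of extended half-life products.

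Residual factor can only raise a measured value, and it appears only in subjects who have recently infused. These are the subjects whose expression is most in question. What is at stake is the size of the estimated change and the threshold proportions. The two ends of the change score also carry different wording: the half-life term appears at baseline and is absent after infusion.

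**Working it through.** The 72 h is a fixed rule, so the plan has no calculated figure to reproduce for it. The nearest calculated figure does not depend on the window and agrees with its statement: n = 70, effect size 0.6, 2-sided alpha 0.025 and a one-sample t-test give a power of 99.6%, against the stated minimum of 95% (Section 14.6).

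**Step 1: how long 5 half-lives takes.** 72 / 5 = 14.4 h, so 72 h covers 5 half-lives only for products with a half-life up to 14.4 h. The fraction of the infused rise that remains at time t is 2^(-t / half-life).

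| Half-life (source) | 5 half-lives | Half-lives elapsed at 72 h | Remaining at 72 h |
|---|---|---|---|
| 8 h (Section 7) | 40 h | 9.0 | 0.2% |
| 12 h (Sections 7, 7.3) | 60 h | 6.0 | 1.6% |
| 18 h (Sections 7, 7.3) | 90 h | 4.0 | 6.3% |
| 19 h (Section 7) | 95 h | 3.8 | 7.2% |

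At exactly 5 half-lives, 2^(-5) = 3.1% remains for any product. If the 50% extension in Section 7.3 is applied to its own 12-18 h, half-lives are 18-27 h, 5 half-lives is 90-135 h, and the residual at 72 h is 6.3-15.7%. The 90-95 h used here is therefore the shorter reading.

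**Step 2: IU/dL attributable to the rule.** The documents give no infused rise. I assume 50-100 IU/dL.

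- Low end (18 h, rise 50): 50 x 0.0625 = 3.1 at 72 h; 50 x 0.03125 = 1.6 at 5 half-lives; difference 1.6.
- High end (19 h, rise 100): 100 x 0.0723 = 7.2 at 72 h; 100 x 0.03125 = 3.1 at 5 half-lives; difference 4.1.

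The excess over a 5-half-life rule is thus about 1.6-4.1 IU/dL for a value drawn right at 72 h, and it shrinks to zero at 90-95 h.

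**Step 3: effect on the subject's median.** During Weeks 37-52 visits are every 2 weeks (Section 12.6), so Weeks 49-52 hold about two values (Weeks 50 and 52). The median of two values is their mean, so one affected value passes on half its excess: 1.6 / 2 = 0.8 to 4.1 / 2 = 2.1 IU/dL. With the whole high-end residual of 7.2 IU/dL the shift is 7.2 / 2 = 3.6 IU/dL.

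Weeks 23-26 have weekly visits, so about four values. Simulation with one of four values raised by 7.2 IU/dL gives an average median shift of about 0.4-1.7 IU/dL (assumed subject levels 5-50 IU/dL, within-subject CV 15-20%). The interim median therefore absorbs most of a single affected value.

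**The case against.** The case against is substantial, and much of it stands.

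- **Carry-over is possible, not established.** A reader might infer that infused factor is routinely counted as expression. That needs an extended half-life product and a sample drawn between 72 h and 90-95 h. The documents give no frequency for either, and products up to 14.4 h are already covered.
- **The baseline contrast is ambiguous.** A reader might infer that baseline must satisfy 5 half-lives. With a bare *or*, 72 h alone meets the rule. On that reading, carry-over at baseline would partly offset the bias in the change. It would not offset the threshold proportions, which use the post-infusion value alone.
- **The wash-out has a limited stated scope.** Section 9.7.2.1 sets aside subjects below 5 IU/dL at Week 16 or back on FVIII, and with prophylaxis 2-3 times a week (Section 7.3) many of their values fall within 72 h anyway. But the exclusion sentence carries no such limit, and these subjects' values have no stated handling. With regular infusions every 84 h, for example, a sample taken just before a dose passes the 72 h rule with 4.1-4.9% of the peak rise present (18-19 h half-life).
- **5 half-lives is not zero.** It leaves 3.1%, so only the increment in Step 2 can be charged to the rule.
- **The Note to File is no contradiction.** Its product-dependent wash-out ("5 days for extended half-life", 3 days for standard products) concerns the start of the bleeding evaluation period. It supports the principle and no more.
- **The text is not the latest.** Amendment 2 and later versions exist, and the Note to File lists FVIII activity as secondary in version 7.0. It also says that the SAP prevails over the protocol on statistical methods. Neither the later endpoint text nor the SAP was available.

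**Conclusion.** The point holds for Amendment 1 as written. By the protocol's own half-lives, 72 h is 3.8-4.0 half-lives for an extended product, and the rule can admit about twice the residual that a 5-half-life rule would (6.3-7.2% against 3.1%). In IU/dL this is about 1.6-4.1 extra per affected value at the cut-off, given an assumed rise of 50-100 IU/dL. It matters most at Weeks 49-52 and little at Weeks 23-26. The direction is upward for the threshold proportions, and upward for the change unless baseline was also taken at 72 h.

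A reader might go further and doubt the significance test of change against zero. The documents do not support that: the shifts are a few IU/dL in some subjects, Section 7.4 reports levels above 50 IU/dL at 52 weeks in most Phase 1/2 subjects at this dose, and the power calculation has a wide margin. The weakness lies in the estimate and the descriptive proportions.

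**What to change.** In the Synopsis (primary endpoint and interim analysis text), Section 9.7.2.1 and Section 14.1.1, exclude post-infusion values obtained within the longer of 72 h and 5 half-lives of the product used. Word footnote b of Table 9.1.1 the same way, as a rule for which values count as baseline in the analysis. In Section 9.7.2.1, state how values are analysed in subjects outside the wash-out's stated scope: those below 5 IU/dL at Week 16 and those who have resumed FVIII. Reconcile the half-life figures in Sections 7 and 7.3, or refer to a product list, so that 5 half-lives has one value per product.

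This changes which values are analysed, not how anyone is treated. The cost is wording and a few more excluded values. Concomitant medication is already recorded on the eCRF (Section 9.4.8) and FVIII treatment in the diary (Section 9.4.8.1). With only about two values at Weeks 49-52, some subjects may lose one or both, so the missing-data rule must cover that case. Before editing, check whether later amendments keep the flat 72 h; if they do, make the change there.

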14.1.2 Procedures for Accounting for Missing, Unused and Spurious Data

Because the completeness of the data affects the integrity and accuracy of the final study analysis, every effort should be made to ensure complete, accurate, and timely data collection and, therefore, avoid missing data.

Sensitivity analyses will be conducted to assess the impact of missing data on the primary efficacy endpoint analysis. Additional details regarding the handling of missing data will be provided in the SAP.

